## 7.4 Efficacy - Exploratory Endpoints Evaluation

All Exploratory efficacy analyses will be performed as described in chapter 6.2 with the FAS only.

Change from baseline for exploratory endpoints (vIGA-ADTM, SCORAD, DLQI, POEM, AIS and PO-SCORAD) will be analysed using mixed model with repeated measures (MMRM) as described in chapter 7.3.

The following parameters will be analysed as described above:

- Absolut proportion of patients achieving a decrease of at least 2 points in vIGA-ADTM in treated population compared to placebo population from baseline to Week 4, 8, 12, 16, 18 and 20.
- Change in proportion of patients achieving a decrease of at least 2 points in vIGA-ADTM from Week 16 to Week 18 and 20.
- Change from baseline in the Dermatology Life Quality Index (DLQI) score in treated population compared to placebo population to Week 4, 8, 12, 16, 18 and 20.
- Change from Week 16 in the Dermatology Life Quality Index (DLQI) score in treated population compared to placebo population to Week 18 and 20.
- Change from baseline in the Patient Orientated Eczema Measure (POEM) score in treated population compared to placebo population to Week 4, 8, 12, 16, 18 and 20.
- Change from Week 16 in the Patient Orientated Eczema Measure (POEM) score in treated population compared to placebo population to Week 18 and 20.
- Change in sleep quality assessment (Athens Insomnia Scale) in treated population compared to placebo population from baseline to Week 4, 8, 12, 16, 18 and 20. The AIS endpoint should be recorded weekly (descriptive values), as defined in section 4.2.11 and p-values only provided for the weeks defined in the endpoint.
- Change in sleep quality assessment (Athens Insomnia Scale) in treated population compared to placebo population from Week 16 to Week 18 and 20. The AIS endpoint should be recorded weekly (descriptive values), as defined in section 4.2.11 and p-values only provided for the weeks defined in the endpoint.
- Change from baseline in the Patient-Oriented SCORAD (PO-SCORAD) score in treated population compared to placebo population to Week 4, 8, 12, 16, 18 and 20.
- Change from Week 16 in the Patient-Oriented SCORAD (PO-SCORAD) score in treated population compared to placebo population to Week 18 and 20.

## 7.5 Safety Evaluation

### Adverse Events

The analyses of AEs with onset on or after first administration of study medication (“treatment-emergent AEs”) will be conducted with the Safety Analysis Set whereas AEs occurring before first application of study medication will only be listed within the Enrolled Set.

The incidence of AEs will be displayed by MedDRA primary SOC and Preferred Term. The counts in these analyses will reflect numbers of patients reporting one or more AE that map to the MedDRA SOC/preferred term.

For AEs with onset during or after administration of first study medication analysis will be performed for the following AE categories:

- All AEs
- Serious adverse events (SAEs)
- AEs with relationship to the study medication
- AEs leading to discontinuation from study (as documented on the AE page)

Furthermore, a summary table with the overall incidences of the above mentioned AEs will be created.

In addition, the analysis of all treatment emergent AEs will also be done by intensity (mild, moderate and severe) displaying patients who reported more than one intensity for one AE under the worst intensity reported.

Furthermore the analysis of AEs and SAEs will also be done by outcome (Recovered/Resolved, Recovering/Resolving, Not Recovered/Not Resolved, Recovered/Resolved with Sequelae, Fatal and Unknown).

The number/percentage of patients with AEs will also be summarized by MedDRA primary SOC and Preferred Term for most frequent non-serious AEs (incidence of preferred term  $\geq 5\%$ ). In this table, the Totals overall or by SOC will consider only those preferred terms with an incidence  $\geq 5\%$ .

All listings will use the Enrolled Set and will include study day of AE onset and AE stop as well as MedDRA information. Note that treatment-emergent AEs are those AEs with an onset at study day 1 or later. Listings will be created for the following topics:

- All AEs
- SAEs
- AEs with relationship to the study medication
- Death (Serious criterion “fatal” or outcome “fatal” documented on the AE page)
- AEs leading to study discontinuation
- AEs before 1st administration of study medication

### **Vital signs**

The analysis of vital sign parameters

- Systolic blood pressure [mmHg]
- Diastolic blood pressure [mmHg]
- Heart rate [beats per min]
- Body temperature [°C]
- Body temperature [°F]

will be performed as described in chapter 6.2 with the Safety Analysis Set (descriptive summary of absolute values and changes from baseline).

### **Physical Examination**

The number and percentage of patients with performed physical examination and the number and percentage of patients with abnormalities during the physical examination will be given within the Safety Analysis Set.

### **Safety laboratory**

The analyses of the safety laboratory will be performed as described in chapter 6.2 with the Safety Analysis Set. The parameters of clinical chemistry and haematology will be analysed in the standardised units reported by the central laboratory.

In addition the number and percentage of patients with normal values, abnormal values with clinical significance and abnormal values without clinical significance will be given for each parameter of clinical chemistry and haematology. The worst value per patient per study will be used.

Laboratory values outside the normal range will be listed in detail.

Additionally, the change of laboratory values in regard to the respective normal ranges (below, within and above) from baseline to the last value (up to week 26) will be displayed in shift tables for each parameter of clinical chemistry and haematology.

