### 8.2 Screening

#### 8.2.1 Screening Visit (Visit 1)

The patient must sign and date the ICF before any study-specific procedures are conducted.

Once informed consent has been obtained, the Investigator will assign a Patient Number (as per Section 10.5) and the following screening procedures/assessments will occur:

- Demographic data
- Medical / surgical history (as detailed in Section 9.2.1)
- Assessment of inclusion/exclusion criteria (Sections 7.2 & 7.3)
- Samples for clinical laboratory safety tests (haematology, serum biochemistry and FSH levels (when applicable) as detailed in Section 9.2.4)
- Sample for pregnancy test (only female patients of child-bearing potential, as detailed in Section 9.2.5)
- Virology (as detailed in Section 9.2.6)
- Vital signs (blood pressures, heart rate and body temperature), as detailed in Section 9.2.3)
- Physical examination (as detailed in Section 9.2.2)
- Body Mass Index (as detailed in Section 9.2.8)
- Body Surface Area (as detailed in Section 9.1.4)
- Validated Investigator's Global Assessment (as detailed in Section 9.1.1)
- Eczema Area and Severity Index (EASI) (as detailed in Section 9.1.2)
- NRS Pruritus Assessment (as detailed in Section 9.1.3)
- Concomitant medication assessment (as detailed in Section 9.2.13)
- Emollient use capture (as detailed in Section 9.2.13.1)

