### 8.3.1 Baseline (Visit 2)

**Note: it must be ensured that inclusion criteria regarding the severity of the disease remain relatively unchanged since screening in order to exclude patients responding to the emollient use since screening visit i.e. IGA score must be unchanged and EASI score should not change by more than 10%.** Patients will attend the investigational site at Visit 2 when the following procedures/assessments will occur.

- Verification of inclusion/exclusion criteria (Sections 7.2 & 7.3)
- Patient Randomisation (as detailed in Section 10.5)
- Samples for clinical laboratory safety tests (haematology and serum biochemistry as detailed in Section 9.2.4)
- Pharmacokinetic Sampling (as detailed in Section 9.2.9)
- Biomarker Sampling (as detailed in Section 9.2.10)
- Vital signs (blood pressures, heart rate and body temperature), as detailed in Section 9.2.3);
- Physical examination (as detailed in Section 9.2.2)
- Electrocardiogram (ECG) (as detailed in Section 9.2.7)
- Dispense Study Drug
- Dispense Patient Compliance Log
- Body Surface Area (as detailed in Section 9.1.4)
- Validated Investigator's Global Assessment (as detailed in Section 9.1.1)
- Eczema Area and Severity Index (EASI) (as detailed in Section 9.1.2)
- NRS Pruritus assessment (as detailed in Section 9.1.3)
- Dermatology Life Quality Index (DLQI) Questionnaire (as detailed in Section 9.1.5)

- Patient Orientated Eczema Measure (POEM) questionnaire (as detailed in Section 9.1.6)
- SCORing AD (SCORAD) questionnaire (as detailed in Section 9.1.7)
- Athens Insomnia Scale (AIS) (as detailed in Section 9.1.8)
- Patient- Orientated SCORAD questionnaire (as detailed in Section 9.1.9)
- Concomitant medication assessment (as detailed in Section 9.2.13)
- Review emollient usage and capture
- AE assessment (as detailed in Section 11)

If all study entry criteria are satisfied the Investigator will randomize the patient and provide the patient with the DS107 capsules or placebo capsules from one of the patient treatment packs available at the site (allocated via the central randomization).

The first administration of DS107 or placebo will be carried out after the Baseline visit. Following this DS107 capsules or placebo medication will be administered once daily. IMP will be administered approximately 2 hours after food consumption at the same time each day. Patients will be instructed to not consume food for approximately 1 hour after IMP administration.

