## 12.7 Safety Analysis

Demographic, medical history and physical examination data will be listed for each patient and summarised descriptively.

All AEs recorded during the study will be coded to system organ class and preferred terms using the current version of the Medical Dictionary for Regulatory Activities (MedDRA). AEs will be tabulated and summarised by treatment, relationship to treatment, seriousness and severity.

Clinical laboratory values (haematology and biochemistry) will be listed for each patient by treatment and day. Values outside the laboratory normal ranges will be listed separately with associated comments as to their clinical significance, with potentially clinically significant abnormalities highlighted and summarised by treatment. Most recent clinical laboratory values obtained prior to dosing will be defined as baseline values.

Individual values of vital signs will be listed and summarised descriptively for each treatment and visit.

Concomitant medications (if any), categorised by medication group and subgroup according to the latest version of the World Health Organisation drug dictionary, will be listed and summarised by treatment.

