14.2.2.6.13	Change in PO-SCORAD score at follow-up (MMRM)	FAS	Change from week 16 in PO-SCORAD score to week 18 and 20	T8.1 T8.2
14.2.2.6.14	PO-SCORAD (Value, Change from Baseline, Change from Wk 16) by visit	FAS	Descriptive statistics by visit	T3a
14.2.3	Further Analyses			
14.2.3.1	Previous medication	SAS	Descriptive statistics by ATC classification (level 1 and 2 and preferred term)	T10
14.2.3.2	Concomitant medication	SAS	Descriptive statistics by ATC classification (level 1 and 2 and preferred term)	T10
14.2.3.3	Reason for Termination	Enrolled Set	Frequency Table	T4
14.2.3.3.1	Reason for Termination	SAS	Frequency Table	T4
14.2.3.4	Screening failure	Non-randomised subjects of the Enrolled Set	Frequency Table	T4
14.3	Safety			
14.3.1	Study medication			
14.3.1.1	DS107 intake duration	SAS	Descriptive statistics	T3
14.3.1.2	Capsules	SAS	Descriptive statistics of number of capsules dispensed	T3
14.3.2	Adverse events			
14.3.2.1	Summary table of Adverse Events	SAS	Frequency table of patients and number of events per AE category	T11
14.3.2.2	Adverse Events by MedDRA SOC and preferred term	SAS	Frequency table	T12

14.3.2.3	Serious Adverse Events by MedDRA SOC and preferred term	SAS	Frequency table	T12
14.3.2.4	AEs related to DS107 by MedDRA SOC and preferred term	SAS	Frequency table	T12
14.3.2.5	AEs leading to study discontinuation by MedDRA SOC and preferred term	SAS	Frequency table	T12
14.3.2.6	AEs by SOC, PT and worst intensity	SAS	Frequency table	T13
14.3.2.7	AEs by SOC, PT and outcome	SAS	Frequency table	T13
14.3.2.8	SAEs by SOC, PT and outcome	SAS	Frequency table	T13
14.3.2.9	Most frequent non-serious adverse events by MedDRA SOC and preferred term	SAS	Frequency table	T13
14.3.5	Vital signs			
14.3.5.1	Vital signs	SAS	Descriptive Statistics	T3a
14.3.5.2	Change in vital signs from baseline	SAS	Descriptive Statistics	T3a
14.3.5.3	ECG	SAS	Descriptive Statistics	T4a
14.3.6	Laboratory values			
14.3.6.1	Clinical Chemistry & Haematology	SAS	Descriptive Statistics	T3a
14.3.6.2	Clinical Chemistry & Haematology per category	SAS	Frequency Table (number and percentage of patients with normal values, abnormal values with clinical significance and abnormal values without clinical significance)	T4a
14.3.6.3	Change in Clinical Chemistry & Haematology	SAS	Shift Table	T14
14.3.7	Physical Examination			

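### As worded, the laboratory abnormality table takes each patient's worst value over the whole study, so pre-dose abnormalities are counted and any difference between arms is diluted

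*SAP*

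**What the plan says.** SAP 7.5, Safety laboratory, specifies a categorical summary: "number and percentage of patients with normal values, abnormal values with clinical significance and abnormal values without clinical significance will be given for each parameter". The next sentence gives the rule for choosing each patient's value: "The worst value per patient per study will be used". The list in SAP Section 8 carries this as table 14.3.6.2, "Clinical Chemistry & Haematology per category", on the Safety Analysis Set, and its description has no time window.

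The Protocol schedules haematology and serum biochemistry at screening (8.2.1), baseline (8.3.1) and Weeks 4, 8 and 16, with a conditional repeat at Week 18 (8.3.7 and the Appendix 1 flow chart). On timing, Protocol 8.3.1 says: "The first administration of DS107 or placebo will be carried out after the Baseline visit". Protocol 12.7 defines a laboratory baseline, "Most recent clinical laboratory values obtained prior to dosing will be defined as baseline values", and SAP 4.1.4 uses the last pre-treatment value for change calculations. Neither is applied to the category table.

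The other planned laboratory outputs are descriptive statistics of values and of differences from baseline, a shift table by reference range from baseline to the last value, and listings of out-of-range values.

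**The concern.** The table should show whether DS107 produces more laboratory abnormalities than placebo. A patient with an abnormal screening or baseline value who is normal at every visit on treatment would still be tabulated as abnormal in the arm to which he or she was later allocated. Such patients say nothing about the drug. Randomisation makes them about equally common in the two arms, so they raise both percentages and draw the ratio toward 1.

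The SAP already separates pre-dose from post-dose events elsewhere. Adverse events are tabulated only if treatment-emergent, and those before first dose are merely listed. The laboratory category table draws no such line. Safety is a stated study objective and laboratory parameters are a named safety variable, so a laboratory signal that is harder to see is a real, if limited, loss.

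**Working it through.** The plan states no figure on this point: no expected rate of abnormal values and no test on the table. The check therefore has two parts, what the wording includes and how counting pre-dose values acts on a comparison. All rates below are assumptions.

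**What is included.** The five routine samples are screening, baseline, Week 4, Week 8 and Week 16. The first dose comes after the baseline visit, so two of the five are pre-dose and three are post-dose. Week 18 is conditional and is left out of the arithmetic.

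**General effect.** For one parameter, let *b* be the share of patients abnormal in a pre-dose sample. Among the rest, let *pc* (placebo) and *pt* (DS107) be the shares who become abnormal after dosing.

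- Whole-study rates: *b* + (1 − *b*)*pc* and *b* + (1 − *b*)*pt*
- Difference: (1 − *b*)(*pt* − *pc*)
- Ratio: closer to 1 than *pt*/*pc* whenever *b* > 0

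The factor (1 − *b*) is relative to the difference among patients who were normal before dosing. If new abnormalities were instead divided by all dosed patients, the difference would equal the whole-study difference, but the ratio would remain *pt*/*pc*. On either denominator the whole-study ratio is the diluted one.

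**Range over *b***, assuming *pc* = 5% and *pt* = 15% (true ratio 3.0):

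| *b* | Placebo | DS107 | Difference | Ratio |
|---|---|---|---|---|
| 0% | 5.0% | 15.0% | 10.0 points | 3.00 |
| 5% | 9.8% | 19.3% | 9.5 points | 1.97 |
| 20% | 24.0% | 32.0% | 8.0 points | 1.33 |
| 40% | 43.0% | 49.0% | 6.0 points | 1.14 |

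**Illustration by sample.** Assume a 5% chance of an abnormal value per sample off drug, 10% on DS107, and independent samples.

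- Three post-dose samples: placebo 1 − 0.95³ = 14.3%; DS107 1 − 0.90³ = 27.1%; ratio 1.9
- All five samples: placebo 1 − 0.95⁵ = 22.6%; DS107 1 − 0.95² × 0.90³ = 34.2%; ratio 1.5
- Pre-dose share: *b* = 1 − 0.95² = 9.75%. The difference goes from 12.8 to 11.6 points, and 12.8 × 0.9025 = 11.6, as the formula requires.

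**What correlation does.** Independence is the unfavourable case. If the same patients tend to be abnormal at every sample, most of those abnormal before dosing are abnormal afterwards too, and the pre-dose samples add fewer extra patients. Those persistent cases would still sit in a table restricted to post-dose values, so a date filter alone is not a full remedy. The result also has to be set against baseline status.

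**Does another output fill the gap?** The shift table uses baseline, but it ends at the last value. An abnormality that appears at Week 4 and has resolved by the last sample is not shown as a shift. For a patient retested at Week 18, the last value may be that retest, taken after dosing has ended. Mean changes and listings give no rate of new abnormality by arm. No planned table counts patients who were normal at baseline and abnormal at any time on treatment.

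**The case against.** The best defence is that the SAP does not name the visits in table 14.3.6.2 and the mock layout it cites (T4a) is not in the documents. That layout is used mostly for by-visit tables elsewhere in Section 8, and a by-visit layout would show baseline separately. This is a fair reason not to treat pooling of pre-dose and post-dose values as established. It does not remove the point: one worst value per patient per study cannot also be a by-visit display, so the specification needs correcting on either reading.

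It can also be said that entry rules limit pre-dose abnormality. White cell counts outside the reference range are excluded at screening, with an exception for mild leucocytosis or leucopenia after consultation. Clinically significant abnormalities and renal or hepatic impairment are handled by exclusions that rest largely on clinical judgement. This stands in part. The effect is probably least for white cells and for the clinically significant category, and falls mainly on abnormal values without clinical significance, for which most parameters have no range-based exclusion.

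The shift table, change summaries and listings are genuine mitigation, so it would be wrong to call the category table the plan's only view of laboratory harm.

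A reader might infer that the physical examination table has the same defect, since "the number and percentage of patients with abnormalities during the physical examination will be given" without a split at first dose. The documents largely answer that. Protocol 9.2.2 has changes from the baseline examination recorded as adverse events, which feed the treatment-emergent tables. The examination is also symptom-directed, so nothing shows that active skin disease would be recorded as an abnormality in every patient.

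**Conclusion.** The point holds for the laboratory category table. As worded, the rule admits two pre-dose samples out of five, and following it attenuates any difference in new abnormalities. The difference shrinks by the factor (1 − *b*) relative to patients normal before dosing, and the ratio moves toward 1. Under the assumed 5% and 10% per-sample rates with independence, the ratio falls from 1.9 to 1.5. Across *b* from 5% to 40%, with assumed new-abnormality rates of 5% and 15%, a true ratio of 3.0 would show as 1.97 down to 1.14. The true *b* is not in the documents, and correlation within patients would reduce the effect of the pre-dose samples.

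A reader might infer that the table is biased in favour of DS107. The documents do not support that: allocation is randomised, so the pre-dose share is similar between arms in expectation, and the result is dilution in either direction. The table is descriptive with no test attached, and no efficacy conclusion depends on it. This is worth correcting before the analysis is programmed, but it does not threaten the trial's main result.

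**What to change.** In SAP 7.5 (Safety laboratory) and the entry for table 14.3.6.2:

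- Replace the whole-study rule with the worst value after the first dose.
- State the end of the window, including whether the conditional Week 18 retest counts.
- Cross-tabulate that worst value against baseline category, by parameter and arm, so that patients normal at baseline who become abnormal can be read off directly. Baseline is already defined in SAP 4.1.4 and Protocol 12.7.
- In the same edit, correct the shift table's reference to values up to week 26, which does not fit a study ending at Week 20.

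The cost is a few SAP sentences, a date filter and a revised table layout. No new data are needed and no other analysis is affected.

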### 8.3.6 Week 16 (Visit 7) / End of Treatment or Early Termination

Patients will return to the investigational site at Visit 7. **The last dose of DS107/placebo should be taken the day before Visit 7.**

For accountability purposes, patients will be required to bring both the used DS107/Placebo patient packs and unused DS107/Placebo supplied at Visit 6. Patients will be required to provide the patient compliance log for confirmation of compliance.

The following procedures/assessments will occur:

- Samples for clinical laboratory safety tests (haematology and serum biochemistry as detailed in Section 9.2.4)
- Pharmacokinetic Sampling (as detailed in Section 9.2.9)
- Biomarker Sampling (as detailed in Section 9.2.10)
- Sample for pregnancy test (only female patients of child-bearing potential, as detailed in Section 9.2.5)
- Vital signs (blood pressures, heart rate and body temperature), as detailed in Section 9.2.3);
- Physical examination (as detailed in Section 9.2.2)
- Electrocardiogram (ECG) (as detailed in Section 9.2.7)
- Body Mass Index (as detailed in Section 9.2.8)
- Collect Study Drug
- Collect and Review Patient Compliance Log
- IMP Accountability (as detailed in Section 10.6)
- Body Surface Area (as detailed in Section 9.1.4)
- Validated Investigator's Global Assessment (as detailed in Section 9.1.1)
- Eczema Area and Severity Index (EASI) (as detailed in Section 9.1.2)
- NRS Pruritus assessment (as detailed in Section 9.1.3)
- Dermatology Life Quality Index (DLQI) Questionnaire (as detailed in Section 9.1.5)
- Patient Orientated Eczema Measure (POEM) questionnaire (as detailed in Section 9.1.6)
- SCORing AD (SCORAD) questionnaire (detailed in Section 9.1.7)
- Athens Insomnia Scale (AIS) (as detailed in Section 9.1.8)
- Patient- Orientated SCORAD questionnaire (as detailed in Section 9.1.9)
- Concomitant medication assessment (as detailed in Section 9.2.13)
- Review emollient usage and capture
- AE assessment (as detailed in Section 11)

The DS107 or placebo patient packs will be returned. No further DS107 or placebo patient packs or patient compliance logs will be issued. Following completion of the study assessments at this visit, there will be continued study restrictions in line with those described in Sections 9.2.12.

An NRS for the assessment of pruritus will continue to be captured on a daily basis from screening to the follow up visits. Emollient use will also continue to be captured on a daily basis for the same period.

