### **8.3.7 Week 18 (Visit 8) / Follow-up 1**

Two weeks after Visit 7 (or early withdrawal visit), patients will return to the investigational site and the follow up procedures/assessments will occur:

- Samples for clinical laboratory safety tests (haematology and serum biochemistry as detailed in Section 9.2.4) – for abnormal values developed during treatment only.
- Vital signs (blood pressures, heart rate and body temperature), as detailed in Section 9.2.3);
- Physical examination (as detailed in Section 9.2.2)

- Body Surface Area (as detailed in Section 9.1.4)
- Validated Investigator's Global Assessment (as detailed in Section 9.1.1)
- Eczema Area and Severity Index (EASI) (as detailed in Section 9.1.2)
- NRS Pruritus assessment (as detailed in Section 9.1.3)
- Dermatology Life Quality Index (DLQI) Questionnaire (as detailed in Section 9.1.5)
- Patient Orientated Eczema Measure (POEM) questionnaire (as detailed in Section 9.1.6)
- SCORing AD (SCORAD) questionnaire (detailed in Section 9.1.7)
- Athens Insomnia Scale (AIS) (as detailed in Section 9.1.8)
- Patient- Orientated SCORAD questionnaire (as detailed in Section 9.1.9)
- Concomitant medication assessment (as detailed in Section 9.2.13)
- Review emollient usage and capture
- AE assessment (as detailed in Section 11)

### 8.3.8 Week 20 (Visit 9) / Follow up 2

Two weeks after Visit 8, patients will return to the investigational site and the final procedures/assessments will occur:

- Vital signs (blood pressures, heart rate and body temperature), as detailed in Section 9.2.3);
- Physical examination (as detailed in Section 9.2.2)
- Body Surface Area (as detailed in Section 9.1.4)
- Validated Investigator's Global Assessment (as detailed in Section 9.1.1)
- Eczema Area and Severity Index (EASI) (as detailed in Section 9.1.2)
- NRS Pruritus assessment (as detailed in Section 9.1.3)
- Dermatology Life Quality Index (DLQI) Questionnaire (as detailed in Section 9.1.5)
- Patient Orientated Eczema Measure (POEM) questionnaire (as detailed in Section 9.1.6)
- SCORing AD (SCORAD) questionnaire (detailed in Section 9.1.7)
- Athens Insomnia Scale (AIS) (as detailed in Section 9.1.8)
- Patient- Orientated SCORAD questionnaire (as detailed in Section 9.1.9)
- Concomitant medication assessment (as detailed in Section 9.2.13)
- Review emollient usage and capture
- AE assessment (as detailed in Section 11)

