# 15 APPENDICES

## 15.1 Appendix 1: Study Flow-Chart

Visit	Screening/ Visit 1	Baseline / Visit 2	Week 1/Visit 3	Week 4/ Visit 4	Week 8 / Visit 5	Week 12/ Visit 6	Week 16/ Visit 7 (EOT)	Week 18/ Visit 8 (Follow up 1)	Week 20/ Visit 9 (Follow up 2)	
Day	-14 to -1	0	7	28	56	84	112	126	140	
Visit Window			+/-2 days	+/-2 days	+/-2 days	+/-2 days	+/-2 days	+/-2 days	+/-2 days	
Type of Visit	Onsite	Onsite	Telephone	Onsite	Onsite	Onsite	Onsite	Onsite	Onsite	
Informed Consent	X									
Assign Patient Identifier Number	X									
Demographics	X									
Medical/Surgical History	X									
Review Inclusion/Exclusion Criteria	X	X								
Randomization		X								
Safety Labs: Serum Biochemistry (including FSH levels at screening when applicable  ), Hematology, Virology	X	X		X	X		X	X 		
Trough Plasma Levels		X		X	X		X			
Biomarker Sampling		X					X			
Pregnancy Test (β-hCG if female of childbearing potential)	X						X			
Vital Signs	X	X		X	X	X	X	X	X	
Physical Examination 	X	X		X	X	X	X	X	X	
ECG		X					X			
BMI	X						X			
Dispense Study Drug 		X		X	X	X				
Collect Study Drug				X	X	X	X			
Dispense Patient Compliance Log		X		X	X	X				
Collect and Review Patient Compliance Log				X	X	X	X			
Discuss Patient Compliance Log			X							
IMP Accountability				X	X	X	X			
Discuss IMP Compliance			X							
BSA	X	X		X	X	X	X	X	X	
vIGA-AD TM	X	X		X	X	X	X	X	X	
EASI Assessment	X	X		X	X	X	X	X	X	
NRS Pruritus Assessment	X-----X									
DLQI Questionnaire		X		X	X	X	X	X	X	
POEM Questionnaire		X		X	X	X	X	X	X	
SCORAD Questionnaire		X		X	X	X	X	X	X	
Athens Insomnia Scale		X-----X								

PO-SCORAD Questionnaire		X		X	X	X	X	X	X
Concomitant Medications	X	X	X 	X	X	X	X	X	X
Emollient Use Capture	X-----X								
Adverse Events 		X	X 	X	X	X	X	X	X

1. FSH requirement to confirm female of non-child-bearing potential for women greater than 40 years of age who have had a cessation of menses for at least 12 months. Non-child bearing potential may also be confirmed via cessation of menses for at least 24 months without FSH levels confirmed.
2. Only if clinically significant change from baseline in safety laboratory results at Week 16.
3. Physical Examination will be symptom-directed.
4. Patients will be instructed to take their last study drug dose the day preceding Week 16 visit.
5. Collection of AEs will start after the first study drug administration.

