#### 4.1.4 Baseline value

The last non-missing value prior to first treatment will be referred to as baseline value and will be used for change from baseline calculations.

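### The laboratory shift table takes each patient's last value, so an off-drug Week 18 retest selectively replaces on-treatment values in patients who had an abnormality, and those who recover show as no shift

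*SAP*

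**What the plan says.** SAP 7.5 (Safety laboratory) states that laboratory change relative to the normal range "from baseline to the last value (up to week 26) will be displayed in shift tables", by parameter; this is table 14.3.6.3. Baseline is defined in SAP 4.1.4: "The last non-missing value prior to first treatment will be referred to as baseline value". Nothing limits the later value to samples taken on treatment.

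The flow chart (protocol Appendix 1) schedules safety laboratory tests for all patients at screening, baseline and Weeks 4, 8 and 16, with none at Week 12. On dosing, protocol 8.3.6 says: "The last dose of DS107/placebo should be taken the day before Visit 7". The Week 18 visit is defined in 8.3.7: "Two weeks after Visit 7 (or early withdrawal visit), patients will return to the investigational site". Laboratory samples at that visit are conditional, and the condition is written in two ways:

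- Protocol 8.3.7: "for abnormal values developed during treatment only".
- Flow chart, footnote 2: "Only if clinically significant change from baseline in safety laboratory results at Week 16".

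SAP 7.5 also plans a frequency table (14.3.6.2) of normal, abnormal clinically significant and abnormal not clinically significant values, for which "The worst value per patient per study will be used". It adds descriptive statistics and a listing of out-of-range values.

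**The concern.** A shift table is read as a summary of what happened to laboratory values under treatment. Here the last value means different things for different patients. For a patient whose results stayed normal it is the Week 16 sample, taken the day after the last dose. For a patient who developed an abnormality it can be the Week 18 sample, taken after about two weeks without drug. Who gets the later sample depends on the outcome being tabulated.

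A drug effect that reverses on stopping would then be under-counted in this table, and a difference between the arms would shrink. Week 16 is also the only scheduled on-treatment laboratory sample beyond eight weeks, the longest treatment in the earlier capsule studies (protocol Table 1). It is therefore the sample one would least want replaced.

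**Working it through.** The plan gives no figure on this point to reproduce, so the check is of calendar and logic, followed by an illustration.

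**Calendar.** Flow-chart days divided by 7:
- last on-treatment sample: 112/7 = Week 16;
- conditional retest: 126/7 = Week 18;
- last visit: 140/7 = Week 20, or 142/7 = 20.3 with the +2 day window.

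Week 26 would be Day 26 × 7 = 182. It matches no visit, and as an upper limit it excludes no scheduled value. It therefore does not keep Week 18 out of the table.

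**Paths.** Take one parameter, within range at baseline, and classify Weeks 4, 8 and 16 as within or above. There are 2 × 2 × 2 = 8 paths, of which 7 have at least one value above. Suppose any Week 18 retest is back within range, and that an above value at Week 16 meets the footnote 2 condition.

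| On-treatment path | Planned table, retest rule of 8.3.7 | Planned table, footnote 2 rule | Last on-treatment value | Worst on-treatment value |
|---|---|---|---|---|
| Above at Week 16 (4 paths) | no shift | no shift | shift | shift |
| Above at Week 4 and/or 8, within at Week 16 (3 paths) | no shift | no shift (not retested) | no shift | shift |
| Never above (1 path) | no shift (not retested) | no shift (not retested) | no shift | no shift |

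Under either rule, all 7 abnormal paths that end in recovery are tabulated as no shift. A shift to the last on-treatment value restores 4 of the 7. A shift to the worst on-treatment value restores all 7. The 3 paths in the middle row are missed by any last-value table; they do not result from the selective retest. These are counts of possible paths, not of patients.

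**Illustration, with assumed rates.** Let A be the patients out of range at Week 16, f the fraction of them retested and r the fraction of those retested who are back in range. Then:

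shifts shown = A × (1 − f × r)

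With 110 per arm (SAP section 2), assume 10% on DS107 (A = 11), A = 2 on placebo, f = 1 and equal recovery in both arms:

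| r | DS107 shown | Placebo shown | Difference |
|---|---|---|---|
| 0 | 11 | 2 | 9 |
| 0.25 | 8.25 | 1.5 | 6.75 |
| 0.50 | 5.5 | 1 | 4.5 |
| 0.75 | 2.75 | 0.5 | 2.25 |
| 1 | 0 | 0 | 0 |

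At 5% or 20% on DS107, A is 5.5 or 22 and falls in the same proportion. The difference shrinks even though recovery is equal in the two arms. If only half are retested (f = 0.5) and half of those recover, 11 becomes 11 × (1 − 0.25) = 8.25.

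**The case against.** The strongest reply is that the abnormality survives elsewhere. The shift table is an additional display. The worst-value table still counts a patient whose value later recovers, so in the illustration it would show all 11. The out-of-range listing (16.2.8.2) shows each such value, and the descriptive statistics of table 14.3.6.1 keep the on-treatment results. Protocol 12.7 also calls for potentially clinically significant abnormalities to be highlighted and summarised by treatment. All of this stands. A reader might infer that reversible laboratory toxicity is concealed or drops out of the report; the documents do not support that. What the reply does not meet is that the worst-value table shows neither the baseline category nor whether the value was low or high, and a listing does not compare arms. Neither replaces a shift table.

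Three further cautions also stand:
- A reader might infer that the worst-value table does count screening and baseline abnormalities. The words "The worst value per patient per study will be used" allow that reading but do not state it, and the table shell is not in the documents.
- Day 126 is the last scheduled sample, not the last possible one. Protocol 9.2.4 allows repeat safety tests. This does not rescue the rule, since a repeat could itself become the last value.
- Retesting every abnormal patient (f = 1) is the extreme case. Under footnote 2, out-of-range values not judged clinically significant would keep their Week 16 result.

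**Conclusion.** The point holds for table 14.3.6.3. As written, the table mixes on-treatment and off-drug values according to whether the patient had an abnormality, and a patient who recovers by Week 18 is tabulated as no shift. This is so under either retest rule. Excursions at Week 4 or 8 that resolve by Week 16 are missed as well, as in any last-value table.

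The size cannot be computed: the documents give no rates of abnormality, retesting or recovery, and the figures above only show how the count behaves under assumed rates. The Week 26 limit by itself changes no result and is a wording error.

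This is a moderate weakness in one descriptive safety table. It has no bearing on the primary endpoints, the significance level or the sample size. It should be corrected because the rule gives a misleading count as written and the data for a correct table are already collected.

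**What to change.** 1. In SAP 7.5 and table 14.3.6.3, tabulate shifts from baseline to (a) the worst on-treatment value after first dose, separately for low and high, and (b) the last on-treatment value, meaning the Week 16 or early-termination sample.
2. Show Week 18 samples and any later repeats in a separate display as recovery data.
3. Delete the Week 26 limit.
4. State that the worst-value rule in table 14.3.6.2 covers values after first dose only.
5. Reconcile the Week 18 retest condition in protocol 8.3.7 with flow-chart footnote 2. One covers any abnormal value arising on treatment, the other only a clinically significant change at Week 16, so sites could differ in which patients are resampled. Which condition applies is for the sponsor to settle.

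The cost is SAP wording, one extra table and, for item 5, aligning two protocol passages. Items 1 to 4 need no new data. The laboratory results may look slightly less favourable.
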